12.2. Sample Size Determination

ANOVA: Repeated measures, within-between interaction has been conducted in order to a priori compute required sample size. As input we estimate ([name], 2020) an effect size f equal to 0.37 with a power $(1-\beta)$ equal to 0.95. Moreover, we considered 9 measurements with at least a correlation among them equal to 0.50 (PID-5-BF reports a test-retest value greater than 0.70). This led to a total sample equal to 12 (critical $F= 2.0563726$; actual power= 0.9785743). By considering at least 10% of withdrawal we

13. DATA MANAGEMENT

13.1. Source Data

Source documents are where data are first recorded, and from which participants' CRF data are obtained. These include, but are not limited to, personal records (from which mental health history and previous treatment may be summarised into the CRF), clinical and office charts, laboratory and pharmacy records, diaries, microfiches, radiographs, and correspondence.

CRF entries will be considered source data if the CRF is the site of the original recording (e.g. there is no other written or electronic record of data). All documents will be stored safely in confidential conditions. On all trial-specific documents, other than the signed consent, the participant will be referred to by the trial participant number/code, not by name.

13.2. Access to Data

Direct access will be granted to authorised representatives from the Sponsor, host institution and the regulatory authorities to permit trial-related monitoring, audits and inspections.

14. QUALITY ASSURANCE PROCEDURES

14.1. Risk assessment

The trial will be conducted in accordance with the current approved protocol, GCP, relevant regulations and standard operating procedures. A risk assessment and monitoring plan will be prepared before the study opens and will be reviewed as necessary over the course of the trial to reflect significant changes to the protocol or outcomes of monitoring activities.

14.2. Monitoring

Regular monitoring will be performed. Data will be evaluated for compliance with the protocol and accuracy in relation to source documents. Following written standard operating procedures, the monitors will verify that the clinical trial is conducted and data are generated, documented and reported in compliance with the protocol, GCP and the applicable regulatory requirements.

14.3. Trial committees

14.3.1 Safety Monitoring Committee

Tages Onlus will conduct a review of all SAEs for the trial reported during the quarter and cumulatively. The aims of this committee include:

- To pick up any trends, such as increases in un/expected events, and take appropriate action
- To seek additional advice or information from investigators where required
- To evaluate the risk of the trial continuing and take appropriate action where necessary

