6. OBJECTIVES AND OUTCOME MEASURES

Objectives	Outcome Measures	Timepoint(s) of evaluation of this outcome measure (if applicable)
Primary Objective To compare the effect of the CMBT-S versus CBT plus standard psychopharmacotherapy for SPD.	
 Change in Personality pathology: Total score at PID-5-BF Schizotypal Personality Disorder Diagnosis: Diagnosis at the 3rd module of SCID-5-PD interview; General Psychopathology: Total score at SCL-90-R; Metacognition: Total score at MAS-A 	9 measurements: (i) at 1 month before intervention starts; (ii) once the treatment starts; (iii) 6 measurements at the end of each month of intervention; at 1-month follow-up; Pre-post evaluation between pre-assessment (1-month before the intervention) and 1-month follow-up assessment.
Secondary Objectives To assess the safety of CMBT-S in patients diagnosed with SPD	
 Dropout rate Completion rate Adverse events (suicidal behaviors, self-harm, psychotic episodes) rate 	At the end of the intervention: dropout rate ($\leq 10\%$ of subjects), completion rate ($\leq 10\%$ of sessions skipped), adverse event rate ($\leq 10\%$ of subjects).

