11. SAFETY REPORTING

11.1. Adverse Event Definitions

Adverse Event (AE)	Any untoward medical occurrence in a participant to whom the intervention has been administered, including occurrences which are not necessarily caused by or related to that treatment.
Serious Adverse Event (SAE)	
A serious adverse event is any untoward medical occurrence that:
 
• results in death• is life-threatening• requires inpatient hospitalisation or prolongation of existing hospitalisation• results in persistent or significant disability/incapacity• consists of a congenital anomaly or birth defect*. 
Other 'important medical events' may also be considered a serious adverse event when, based upon appropriate medical judgement, the event may jeopardise the participant and may require medical or surgical intervention to prevent one of the outcomes listed above.
 
NOTE: The term "life-threatening" in the definition of "serious" refers to an event in which the participant was at risk of death at the time of the event; it does not refer to an event which hypothetically might have caused death if it were more severe.

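### The quarterly safety review names only SAEs as its input, but the trial's safety outcome is three event types regardless of seriousness, so non-serious cases need not reach the committee

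*Combined protocol and SAP*

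**What the plan says.** Three places in the combined protocol and SAP bear on this.

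- **Section 14.3.1 (Safety Monitoring Committee)** states what is reviewed: "Tages Onlus will conduct a review of all SAEs for the trial reported during the quarter and cumulatively". No other class of event is named. The committee's aims include "To pick up any trends, such as increases in un/expected events, and take appropriate action", asking investigators for more information, and weighing the risk of letting the trial continue.
- **Section 6 (Objectives and Outcome Measures)** gives the safety objective as "To assess the safety of CMBT-S in patients diagnosed with SPD". Its event outcome is "Adverse events (suicidal behaviors, self-harm, psychotic episodes) rate", with no seriousness condition. The timepoint entry opens with "At the end of the intervention: dropout rate" and goes on to give benchmarks for dropout, completion and adverse events. For adverse events the benchmark is at most 10% of subjects. It does not say which subjects form the denominator.
- **Section 11.1 (Adverse Event Definitions)** defines an SAE by outcome: death, threat to life, disability, congenital anomaly, or an event that "requires inpatient hospitalisation or prolongation of existing hospitalisation". It adds a limb that depends on judgement: "Other 'important medical events' may also be considered a serious adverse event when, based upon appropriate medical judgement". The three Section 6 event types are not named as SAEs.

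Section 11 contains definitions only. It has no rule for passing non-serious events to the committee. Monitoring under Section 14.2 concerns protocol compliance and agreement with source documents, not event rates.

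**The concern.** The scope of the only interim safety review described does not match the safety outcome that the protocol chose. Self-harm without admission, suicidal behaviour that did not put life at risk at the time, or a psychotic episode managed without admission can each count towards the Section 6 outcome and still not be an SAE. Whether the committee hears of such an event then depends on someone classing it as an important medical event.

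Participant safety is at stake. The synopsis has recruitment running from 15 December 2020 to 30 September 2021, about nine and a half months, against six months of treatment. Early participants can therefore have events while others are still being enrolled. If the committee sees only SAEs, it may weigh the risk of continuing without the events that the protocol names as its safety measure. In a trial of 14 people a handful of such events is the whole signal.

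**Working it through.** **1. Arm size.** The arithmetic needs only the sample size, so the plan's own figure was reproduced first. Section 12.2 gives f = 0.37, 9 measurements and correlation 0.50. There are two groups. Alpha is not stated; 0.05 is assumed.

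- Noncentrality: f² × N × m / (1 − rho) = 0.37² × 12 × 9 / 0.50 = 29.57
- Degrees of freedom: (2 − 1)(9 − 1) = 8 and (12 − 2)(9 − 1) = 80
- Critical F = 2.0564 and power = 0.9786, matching the stated 2.0563726 and 0.9785743
- With 10% withdrawal: 12 / 0.90 = 13.3, rounded up to 14, matching the synopsis

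With 1:1 allocation (Section 7) this is about 7 per arm.

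**2. Which events reach the review.** Setting Sections 6, 11.1 and 14.3.1 side by side:

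| Section 6 event | Counts towards the safety outcome | In the stated review input |
|---|---|---|
| Meets an outcome limb of 11.1 | Yes | Yes |
| Meets none, judged an important medical event | Yes | Yes, by discretion |
| Meets none, not so judged | Yes | No |

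The third row is the gap.

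**3. How few events matter against 10%.** Section 6 gives no denominator, so both readings are shown.

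| Affected participants | CMBT-S arm of 7 | All 14 |
|---|---|---|
| 1 | 1/7 = 14.3% (above) | 1/14 = 7.1% (within) |
| 2 | 2/7 = 28.6% (above) | 2/14 = 14.3% (above) |

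The random-number scheme in Section 9.4 does not guarantee 7 per arm. The per-arm result changes only if the arm reaches 10: 1/9 = 11.1% is above the benchmark and 1/10 = 10.0% meets it.

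**4. Illustration with assumed rates.** The documents give no event rate. Assume a per-participant risk p = 10%, and let s be the share of affected participants whose events are SAEs. The chance that the benchmark is exceeded while no SAE occurs is:

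- n = 7 (one or more affected): (1 − ps)⁷ − (1 − p)⁷. For s = 25%: 0.975⁷ − 0.9⁷ = 0.359. For s = 75%: 0.925⁷ − 0.9⁷ = 0.101.
- n = 14 (two or more affected): (1 − ps)¹⁴ − (1 − p)¹⁴ − 14p(1 − s)(1 − p)¹³. For s = 25% this is 0.206; for s = 75% it is 0.018.

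Under these assumptions the range is 36% down to 10% on the per-arm reading, and 21% down to 2% on the whole-trial reading.

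**The case against.** The case on the other side has real substance.

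- *The SAE definition may catch these events.* The important-medical-event limb is a natural home for suicidal behaviour, self-harm or a psychotic episode. This narrows the gap. It does not close it, because the limb is permissive and may be applied differently by different centres.
- *The committee is not confined to SAEs.* Section 14.3.1 never says so. One aim speaks of events in general, the list of aims is open-ended, and the committee may ask investigators for more. Section 14.1 also promises a risk assessment and monitoring plan whose content is not given. So SAEs-only is an inference from the one stated input, and a wider practice is possible. Nothing in the text requires it.
- *The events would not go unnoticed.* A reader might infer that they stay hidden until treatment ends. The documents do not support that: the synopsis provides 24 weekly sessions, and Section 11.1 defines non-serious adverse events. What is missing is a stated aggregate review by the committee before the end-of-intervention figure.
- *The 10% is not a limit that the committee enforces.* A reader might infer that one self-harm event breaks a protocol limit. Section 6 lists the figure as an outcome benchmark beside dropout and completion, ties no action to it, and gives no denominator. On the whole-trial reading one event is within it.
- *The benchmark is coarse.* At an assumed 10% risk it is exceeded with probability 1 − 0.9⁷ = 52% for n = 7. That is a weakness of the benchmark at this sample size, and exceeding it is not by itself reliable evidence of harm.

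**Conclusion.** The point stands as a mismatch of scope. Read as written, Section 14.3.1 can leave out events that Section 6 makes the trial's safety outcome, and no other section assigns their review before the end of the intervention. One non-serious case (CMBT-S arm of about 7) or two (all 14) could exceed the 10% benchmark without appearing in the SAE review.

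This rests on taking SAEs as the full input because nothing else is named, on some Section 6 events being non-serious and not classed as important medical events, and on roughly equal arms for the per-arm figure. The probabilities in the working are illustrations under assumed rates; the finding does not depend on them. The documents do not support the stronger conclusions that the committee is barred from seeing these events, that nobody would know of them, or that a stopping limit has been set and can be crossed. The change should be made: it is small and it concerns participant safety.

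**What to change.** Reconcile Sections 6, 11.1 and 14.3.1. In 14.3.1, extend the review to all SAEs plus every event in the three Section 6 categories, serious or not, for the quarter and cumulatively. The committee and its frequency can stay as they are. Section 6 should also say whether the 10% refers to the CMBT-S arm or to all participants.

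Listings should be pooled or by coded arm. Section 14.3.1 gives the review to the sponsor, whereas Section 9.4 keeps the allocation from the investigators and Section 9.5 declares participant, care provider and outcome assessor blinded. Listings under open treatment labels would put that at risk.

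The cost is a sentence or two of protocol text, a slightly longer quarterly listing for 14 participants, and prompt recording of these events during treatment instead of compiling them at its end. No stopping rule is implied.

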15. PROTOCOL DEVIATIONS

A trial related deviation is a departure from the ethically approved trial protocol or other trial document or process (e.g. consent process or IMP administration) or from Good Clinical Practice (GCP) or any applicable regulatory requirements. Any deviations from the protocol will be documented in a protocol deviation form and filed in the trial master file.

16. ETHICAL AND REGULATORY CONSIDERATIONS

16.1. Declaration of Helsinki

The Investigator will ensure that this trial is conducted in accordance with the principles of the Declaration of Helsinki.

16.2. Guidelines for Good Clinical Practice

The Investigator will ensure that this trial is conducted in accordance with relevant regulations and with Good Clinical Practice.

16.3. Approvals

Following Sponsor approval the protocol, informed consent form, participant information sheet will be submitted to an appropriate Research Ethics Committee (REC), HRA (where required), regulatory authorities (MHRA in the UK), and host institution(s) for written approval.

The Investigator will submit and, where necessary, obtain approval from the above parties for all substantial amendments to the original approved documents.

16.4. Reporting

The CI shall submit once a year throughout the clinical trial, or on request, an Annual Progress Report to the REC, host organisation, funder (where required) and Sponsor. In addition, an End of Trial notification and final report will be submitted to the REC, host organisation and Sponsor.

16.5. Participant Confidentiality

The study will comply with the General Data Protection Regulation (GDPR) and Data Protection Act 2018, which require data to be de-identified as soon as it is practical to do so. The processing of the personal data of participants will be minimised by making use of a unique participant study number only on all study documents and any electronic database(s), with the exception of the CRF, where participant initials may be added. All documents will be stored securely and only accessible by study staff and authorised personnel. The study staff will safeguard the privacy of participants' personal data.

17. FINANCE AND INSURANCE

17.1. Funding

Tages Onlus will be the only institution financially supporting the study.

17.2. Insurance

Tages Onlus and single therapists are legally liable for the negligent acts and omissions of their employees. If participants are harmed whilst taking part in a clinical trial as a result of negligence on the part of a member of the trial team this liability cover would apply. In exceptional circumstances an ex-gratia payment may be offered.

18. PUBLICATION POLICY

IPD will be released at the end of the study and will be accessible permanently. Individual participants data underline the results in all the future publications related to the trial will be available after deidentification.

